6.3 HYPOTHESES AND DECISION RULES

As the objective of this study is to characterize the safety and tolerability of escalating doses of Scop HBT, three sets of safety endpoints will be compared statistically between placebo and active dosing groups. Some PK parameters will also be compared statistically across dose levels. Table 7 describes the hypothesis testing pre-specified in the statistical analysis.

The null hypothesis of no worse scores for Injection Site VAS (pain, itching, tingling, numbness); change in BPRS Score (6 hours, 48 hours, 8 days); change in DSST (48 hours, 8 days); and C-SSRS (SD 8) between dose levels of active Scop HBT and placebo will be tested statistically using a one-sided alternative of worse (higher for C-SSRS, VAS, and BPRS, lower for DSST scores for Scop HBT vs. placebo). Each dose level will be tested against the same placebo group (all participants receiving placebo). Methods for analysis of neuropsychiatric scales and injection site reactions are described in Sections 6.13.4 [6.14.6](#) and [6.14.8](#), respectively.

For PK parameters, variation across doses will be tested for T_{max} , $t_{1/2}$, V_d/F , Cl_F , and MRT against the null hypothesis of no difference across doses. A joint significance test (1 test per parameter) will be used.

Dose-proportionality will be tested using the dose-normalized parameters $C_{max}/Dose$ and $AUC_{\infty}/Dose$. A likelihood ratio test will be used for testing the joint null hypothesis of equivalence across all doses using a two-sided alternative. Each dose level will also be tested against the next dose level using a two-sided test. The methods for analysis and hypothesis testing are described in Section - [6.15](#). A total of 110 hypothesis tests will be performed. Procedures for multiple comparisons are detailed in Section [6.8](#).

Table 7: Pre-Specified Hypothesis Tests

Drug Characteristic	Null Hypothesis	Relevant Endpoints [Count]	Number of Comparisons Per Parameter	Total Number of Hypothesis Tests
Safety	Equivalence with Placebo	Injection site VAS (pain, itching, tingling, numbness) x (10-45 minutes, 1-5 hours, 8-48 hours) [12] Change in BPRS score from baseline (6 hours, 48 hours, SD 8) [3] Change in DSST scores from baseline (48 hours, SD 8) [2]	5 (Each dose level vs. Placebo)	90

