Safety	Equivalence with Placebo	C-SSRS (SD 8) [1] Change in DSST scores from baseline (48 hours, SD 8) [2] Proportion with lower raw DSST scores compared to baseline (48 hours, SD 8) [2]	1 (All dose levels vs. Placebo)	5
PK Dose-Equivalence	Equivalence across doses	T_{max} , $t_{1/2}$, V_d/F , MRT, Cl_F	1 Joint Test	5
PK Dose-Proportionality	Equivalence across doses	$C_{max}/Dose$ $AUC_{\infty}/Dose$	1 (joint test) 4 (each dose vs. next higher dose)	10
Total				110

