6.10 DISTRIBUTIONAL ASSUMPTIONS

The residuals of ANOVA models will be assessed for normality using a Shapiro-Wilk test in conjunction with visual inspection of quantile-quantile plots. Lognormality is commonly assumed for PK parameters. If the normality assumption is not met, logarithmic (natural or base-10) transformation will be assessed. If lognormality is rejected, non-parametric bootstrap replication with a minimum of 10,000 replications will be used to calculate confidence intervals and perform hypothesis testing.

With small samples, the normality of parameters, such as the sample mean, cannot be assured. Therefore, quantile-based confidence intervals will be obtained, and hypothesis testing will be conducted using comparisons of observed test statistics to test statistics obtained under the null hypothesis. For hypotheses of equivalence between two populations (e.g. placebo and dosage groups, $\beta_1 = 0, \mu_1 = \mu_2$), an unequal sample unequal variance T-statistic will be used:

$$T = \frac{\widehat{\mu}_1 - \widehat{\mu}_2}{s_p \sqrt{\frac{1}{n_1} + \frac{1}{n_2}}} \quad (1)$$

where, $\widehat{\mu}_1$ and $\widehat{\mu}_2$ are the observed sample means, and

$$s_p = \sqrt{\frac{(n_1-1)s_1^2 + (n_2-1)s_2^2}{n_1+n_2-2}} \quad (2)$$

Where s_1^2 and s_2^2 are the sample variances. The null distribution will be generated by resampling from the values at their two groups shifted to their pooled sample mean.

For joint significance tests (e.g. $H_0: \beta_1 = \beta_2 = \beta_3 = \beta_4 = 0$), the F-statistic will be used with the formula,

$$F_b = \frac{\left(\frac{RSS_1 - RSS_2}{p_2 - p_1}\right)}{\left(\frac{RSS_2}{n - p_2}\right)} \quad (3)$$

where RSS_1 is the residual sum of squares for an ANOVA model fit under the null with p_1 parameters and RSS_2 a model fit with all parameters p_2 included. The null distribution will be generated through resampling from the distributions of each dosage cohort shifted to their common mean. With bootstrap resampling, p-values will be calculated by comparing observed values of the test statistic to the null distribution:

$$p = \frac{1}{B} \sum_{b=1}^B I(F_b \geq F_{obs} \text{ or } |T_b| \geq |T_{obs}|) \quad (4)$$

where B is the number of bootstrap samples taken.

ANOVA also assumes homogeneity of variance (i.e. homoskedasticity). Homogeneity of variance will be assessed. If variances are equal, homogenous variance ANOVA will be

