6.14.6 Neuropsychiatric Scales

Descriptive statistics (mean, standard deviation, minimum, maximum, median) of scores on the neuropsychiatric status assessments (BPRS and C-SSRS) will be presented for each timepoint by dosing group (placebo, 0.005, 0.007, 0.011, 0.014, 0.021mg/kg).

As the RASS will only be used if general agitation or sedation are reported, the number of participants with RASS performed, the reason for performance of the RASS, the time since injection when the RASS was administered, the RASS score, the resulting action taken (e.g., rescue drug administered, resolved or unresolved) will be presented by dose group and overall.

Signal neuropsychiatric events defined as DLTs (BPRS ≥ 40 or item score ≥ 4 at 48-hour post-dose evaluation) or symptoms (e.g., delirium, paranoia, and/or hallucinations) defined as adverse events will be noted and the affected participants' BPRS, C-SSRS, and RASS (if applicable) scores will be presented at each time point in relation to the determination of the event.

Change in BPRS scores from baseline (when BPRS≤25) will be compared for each dose level to placebo. Each time-point will be modeled separately. Changes in BPRS scores will be compared between each dose and the placebo group using a Wald test of coefficients from ANOVA.

Change in C-SSRS scores at SD 8 (from a baseline of zero) will be assessed. The proportion of individuals having a change in score from zero will be compared for each drug dosage level to the placebo group using Fisher's exact test. Scores for all participants receiving active Scop HBT will be compared to those receiving placebo.

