6.14.7 Assessment of Cognitive Impairment

The DSST will be used to measure cognitive impairment due to Scop HBT. The raw score will be calculated from the difference in total number of trials attempted and the number of trials incorrect. Summary statistics for raw DSST scores (mean, median, min, max, standard deviation, 95% confidence intervals) will be presented over time by dose level. The proportion of individuals with declines in raw scores between baseline and 48 hours and baseline and Day 8 will be compared between active placebo and active Scop HBT using a Fisher's Exact Test. This test will be conducted once for all participants receiving active Scop HBT and all participants receiving placebo.

In addition, individual changes in DSST scores between baseline and 48 hours and SD 8 will be compared between each dosage cohort and placebo and for all active dosages and placebo. Equation 5 presents the model that will be used to compare DSST scores by cohort,

$$G(Y_i) = \beta_0 + \beta_1 \times I(D_i = 1) + \beta_2 \times I(D_i = 2) + \beta_3 \times I(D_i = 3) + \beta_4 \times I(D_i = 4) + \beta_5 \times I(D_i = 5) + \varepsilon_i \quad (5)$$

where $Y_{i,}$ is the change in DSST scores at 48 hours or SD 8, D_i is the dosage level for participant i ($1=0.005, 2=0.007, 3=0.011, 4=0.014, 5=0.021 \text{ mg/kg}$), β_0 is the change in DSST scores for placebo participants, and ε_i is the error term for each participant i . Wald tests will be used for the null hypotheses of no differences between active Scop HBT and placebo: $\beta_1 = 0, \beta_2 = 0, \beta_3 = 0, \beta_4 = 0, \beta_5 = 0$.

Equation 6 shows the model that will be used to test the null hypothesis of no differences between all levels of active Scop HBT compared to placebo

$$G(Y_i) = \beta_0 + \beta_1 \times I(D_i \in \{1,2,3,4,5\}) + \varepsilon_i \quad (6)$$

A Wald test will be used to test the null hypothesis that there are no significant differences in the change in DSST scores between active and placebo Scop HBT ($\beta_1 = 0$) in Eq. 6.

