6.14.8 Assessment of Injection Sites

Descriptive statistics of injection site assessments will be reported. Mean, median, standard deviation, minimum, and maximum VAS scores will be presented for each time-point by dosing group (placebo, 0.005, 0.007, 0.011, 0.014, 0.021mg/kg).

Frequencies of severity (None, Mild, Moderate, Severe, Potentially Life Threatening) from injection site assessments performed by clinicians will be summarized by type (pain, tenderness, Erythema/Redness, Induration/Swelling) and timepoint, by dosage group.

Differences between placebo and active Scop HBT injection site VAS scores will be compared statistically by dosage level using three different ANOVA models corresponding to the first hour, next 4 hours, and 8 – 48 hours after injection. In the first model, VAS scores will be averaged over 10, 15, 30, & 45 minutes. In the second model, VAS scores will be averaged over 1, 1.5, 3, and 5-hour timepoints. The third model will include VAS scores averaged over 8, 12, 24, and 48-hour timepoints. VAS scores for active Scop HBT doses will be tested against scores for placebo using a one-sided alternative of higher scores for Scop HBT than placebo.

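### SAP 6.10 Eq. 4 gives a two-sided bootstrap p-value for per-dose placebo comparisons that SAP 6.3 and protocol 12.1.2 define as one-sided

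*SAP*

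**What the plan says.** **The fallback.** SAP 6.10 first checks ANOVA residuals for normality, then tries a log transformation. After that, "If lognormality is rejected, non-parametric bootstrap replication with a minimum of 10,000 replications will be used" for confidence intervals and hypothesis tests. For two-group hypotheses, with placebo against dose groups as the example, it prescribes a T-statistic (Eq. 1-2). Then: "With bootstrap resampling, p-values will be calculated by comparing observed values of the test statistic to the null distribution". Eq. 4 is the only p-value formula given: the share of resamples with `F_b ≥ F_obs` or `|T_b| ≥ |T_obs|`.

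**The hypotheses.** SAP 6.3 takes injection site VAS, BPRS change, DSST change and C-SSRS against placebo and says the null hypothesis "will be tested statistically using a one-sided alternative of worse", meaning higher for VAS and BPRS and lower for DSST. SAP 6.14.8 repeats this for VAS, "using a one-sided alternative of higher scores for Scop HBT than placebo". Protocol 12.1.2 sets a one-sided alternative for BPRS change, DSST change and VAS. For the PK dose-proportionality parameters SAP 6.3 says the opposite: "Each dose level will also be tested against the next dose level using a two-sided test".

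**Where direction is missing.** SAP 6.14.6 says only "Changes in BPRS scores will be compared between each dose and the placebo group using a Wald test of coefficients from ANOVA", and SAP 6.14.7 only "Wald tests will be used for the null hypotheses of no differences between active Scop HBT and placebo".

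**The concern.** An absolute value in Eq. 4 suits the adjacent-dose PK tests, which are two-sided. It does not suit the safety comparisons, which ask only whether active is worse. A programmer following Eq. 4 and one following 6.3 would report different p-values from the same data, and no section gives a directional bootstrap version.

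Two things are at stake on the fallback path. Some results in the harmful direction that would be marked at 0.05 one-sided would not be marked. A result favouring active could be marked significant under a hypothesis that allows only harm. SAP 6.8 says it chose a lenient false discovery rate so that marginal findings, including safety findings, are not missed; a two-sided p-value for a harm-only question works against that aim.

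**Working it through.** **1. Tests exposed (SAP Table 7).** VAS: 4 scales × 3 windows × 5 doses = 60. BPRS change: 3 × 5 = 15. DSST change: 2 × 5 = 10. Total 60 + 15 + 10 = 85 of 110. C-SSRS and the proportion with DSST decline use Fisher's exact test, so Eq. 4 does not touch them.

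**2. The SAP's own thresholds.** Benjamini-Hochberg, i × 0.20 / 110 for i = 1 to 5: 0.0018, 0.0036, 0.0055, 0.0073, 0.0091. These match SAP 6.8.

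**3. One statistic, symmetric null.** Take T as active minus placebo, 6 active and 10 pooled placebo (SAP 3.4 minimum), with Student t on 6 + 10 − 2 = 14 df standing in for the bootstrap null.
- T = 1.9 (harm): one-sided p = 0.039, two-sided p = 0.078.
- T = −2.5 (active better): one-sided p = 0.987, two-sided p = 0.025.

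**4. One skewed data set.** Invented values: active 4, 6, 3, 9, 2, 14; placebo 1, 0, 3, 2, 0, 5, 1, 2, 4, 8. The means are 6.333 and 2.6. Pooled variance = (101.33 + 56.4) / 14 = 11.27, so the pooled SD is 3.357. T = 3.733 / (3.357 × √(1/6 + 1/10)) = 2.15. With the 6.10 resampling (200,000 draws), the one-sided p is 0.032 and Eq. 4 gives 0.101. The lower tail adds 0.101 − 0.032 = 0.069, more than the upper tail itself. With skewed data Eq. 4 can therefore do more than double the p-value.

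**5. Simulated chance of reaching the fallback and p < 0.05 for harm.** The documents give no distributions, so all inputs are assumed. Base case: one VAS value per subject, zeros in 70% of placebo and 30% of active, otherwise 0.1 + exponential (mean 1.5 cm), capped at 10. Fallback means Shapiro-Wilk p < 0.05 on the residuals, with the log step taken as unusable because of zeros. There were 1,500 trials of 1,500 resamples.

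| Assumed VAS-like data, 6 v 10 unless stated | Eq. 4 | One-sided |
|---|---|---|
| Base case | 5% | 24% |
| Base case, 10,000 resamples (SAP minimum; 1,000 trials) | 5% | 23% |
| Mean of four time points; 30% of placebo and 70% of active react | 3% | 22% |
| Mean of four independent time points | 13% | 23% |
| Base case, log(x+1) must also be rejected | 2% | 13% |
| Four-point mean, log(x+1) also rejected | 2% | 19% |
| Four independent points, log(x+1) also rejected | 3% | 5% |
| Base case, 9 v 15 | 12% | 33% |
| Base case at threshold 0.0091 | 0.5% | 2.5% |
| Zeros 70% placebo, 50% active | 0.6% | 10% |
| Zeros 50% in both (no true difference) | 0.3% | 3.7% |

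Repeats of the base case with other seeds gave 4 to 5% against 21 to 25%. When active is truly better (zeros 30% placebo, 70% active), Eq. 4 flags an improvement in 13 to 16% of trials; the one-sided form flags harm in 0.1% or fewer. BPRS-like data gave 6% against 18% when 60% of active subjects rise, and 30% against 33% when 90% rise.

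**The case against.** **6.3 governs.** SAP 6.1 sends the reader to 6.3 for the hypotheses, and 6.10 is a general section whose single formula covers F and T together. A statistician could take the direction from 6.3. This supports one-sided as the intent. It does not change a formula that carries an absolute value in a section naming the placebo comparison, and 6.14.6 and 6.14.7 supply no direction. The rule in SAP Section 1 that the SAP overrides the protocol does not settle it either, because the conflict lies within the SAP.

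**The fallback rate is uncertain.** SAP 6.10 pairs Shapiro-Wilk with visual inspection, states no cut-off, and does not say how zeros enter the log step. This stands, and it is why the log(x+1) rows are shown.

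**The effect inputs are not grounded.** Protocol 7.4.1 lists the same excipients for active and placebo, so a large local difference is not a given. This also stands; the gap shrinks with the assumed difference.

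**Little depends on these tests.** SAP 6.1 calls testing limited, SAP 6.8 calls the trial exploratory, and protocol 12.3 and SAP 6.7.2 keep statistical tests out of halting and termination decisions. Descriptive statistics by dose are reported regardless, and the quantile-based intervals in 6.10 would show the direction of a flagged result. All of this stands and limits the weight of the point.

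**Conclusion.** SAP 6.10 Eq. 4 contradicts SAP 6.3, SAP 6.14.8 (VAS) and protocol 12.1.2 for the per-dose VAS, BPRS-change and DSST-change tests. The conflict applies only where normality and lognormality are both rejected. That is most plausible for the 60 VAS tests, whose scores are bounded at 0; it is possible for BPRS change and not shown for DSST change. The ceiling of 85 tests would be reached only if every such model fell back. At nominal 0.05 the loss can be sizeable under the assumed data (about 4 to 5% against about 24%). It is smaller with log(x+1) and small at the fifth Benjamini-Hochberg threshold.

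A reader might infer three stronger points that the documents do not support.
- *The fallback causes one- and two-sided p-values to be mixed in the Benjamini-Hochberg list.* Table 7 already puts one-sided safety tests and two-sided PK tests in one list, and correcting Eq. 4 leaves that unchanged.
- *The two pooled DSST-change tests are also affected, making 87.* Protocol 12.1.2 attaches the one-sided alternative to each dose level and adds the pooled analysis without a direction. SAP 6.14.7 Eq. 6 gives none, and 6.3 speaks of dose levels against placebo. Their sidedness is unstated.
- *Subject protection or dose escalation is weakened.* No stopping or escalation rule uses these tests.

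**What to change.** In SAP 6.10, define T as active minus placebo and split Eq. 4 by test:
- VAS and BPRS change, per dose: `I(T_b ≥ T_obs)`.
- DSST change, per dose: `I(T_b ≤ T_obs)`.
- PK adjacent-dose comparisons: keep `|T_b| ≥ |T_obs|`.
- Joint tests: keep F.

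State the same one-sided direction for the per-dose Wald tests in 6.14.6 and 6.14.7. For the pooled DSST-change test, state whether the 6.3 one-sided alternative applies and match Eq. 4 to the answer.

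The cost is SAP wording and one formula, with no new data, visits or subjects. It should be done before unblinding, since SAP 6.2 treats later changes to the analyses as post hoc.

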6.11 EXTENT OF EXPOSURE AND TREATMENT COMPLIANCE

This is a single dose study where the treatment is given in a single IM injection. The study medication (active or placebo) will be prepared by the pharmacist in accordance with the Drug Preparation Manual. Therefore, exposure will be closely monitored, and treatment compliance is not a major risk.

In the event that rescue medications (physostigmine, atropine, diazepam or lorazepam) are administered, data for the participant will be analyzed according to the dosage of Scop HBT received for measures taken up to the administration of the rescue medication. Thereafter, participant data will be treated differently by endpoint. Data collected after administration of the rescue medication for the BPRS, DSST, and/or RASS will be censored in analyses, though presented descriptively. Adverse events, injection site VAS, and PK data will not be censored.

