9.1.3. Biological Samples

Samples collected under this protocol will be used to conduct protocol-related safety and PK evaluations. No genetic testing will be performed on these samples.

Plasma for PK evaluations will be stored at Battelle Memorial Institute in a quality-controlled environment. Transport and storage of these biological samples will be handled according to institute SOPs. Any study for the future use of these biological samples will have IRB/Human Use Committee approval. In addition, a subject may decide at any point to withdraw consent for the future use of his or her samples. Should a subject withdraw consent for the use of his or her samples, the samples will be destroyed according to institute SOPs.

9.2. **Rescue Medications and Concomitant Medications**

This protocol places restrictions on all medication use during the study including the use of rescue medications. The PI will recommend medication for symptomatic relief, if necessary.

9.2.1. **Rescue Medications**

Physostigmine should be used as needed to reverse the effects of scopolamine in any instance where there is a concern that the symptoms may result in harm (self-induced or otherwise) to the subject or a concern that the subject may pose a risk to others. The following circumstances would indicate a need for physostigmine treatment:

- A rating of severe (ie, score of 5 or greater) on any of the following 5 items on the BPRS:
 - #4 Suicidality
 - #5 Hostility
 - #10 Hallucinations
 - #11 Unusual Thought Content Item
 - #12 Bizarre Behavior
- Severe agitation (score of 3 or greater) on the RASS

A physician investigator must make the determination to administer physostigmine. Administration may be performed by a physician, physician assistant, or nurse; however, a physician must be present to evaluate the response and determine the need for additional treatment.

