If used, a physician, physician assistant, or nurse will administer 0.5 mg physostigmine IV over 1 minute, which may be repeated every 5 minutes until a total dose of 2 mg has been given (ie, a total of 4 doses). Atropine and a benzodiazepine (eg, diazepam or lorazepam) should be at the bedside in case of bradycardia or seizures. If the subject is not already on continuous cardiovascular monitoring when physostigmine is administered, the subject will be placed on continuous monitoring of ECG (3-lead) and vital signs (refer to Section 11.1.2 for details). The effects of physostigmine last only 1-2 hours; therefore, a repeat dose may be necessary.

If there is an adequate response to treatment with physostigmine, the event should be considered a nonextreme DLT; however, if there is not an adequate response to treatment, the event should be considered an extreme DLT (refer to Section 7.6.1 for further detail regarding procedures related to DLTs).

When a physician investigator determines that physostigmine administration is necessary, the following will be recorded in the subject's record to ensure adequate information is available for evaluation of the associated DLTs by the PI, research monitor, DSMB members, and the sponsor's PVG physician:

- Study day and date (to be recorded by study staff)
- Circumstance(s) indicating the need for treatment (see above) and physician investigator's authorization to administer physostigmine

- For each dose given, the following will be recorded:
 - Dose number (eg, 1-4), dose administered (mg; see above), and start and stop times of administration (to be recorded by staff member administering the dose)
 - Response to treatment, and reason(s) for administering an additional physostigmine dose, if needed
- Total number of physostigmine doses (1-4) and total dose (mg) administered
- Whether the overall response to physostigmine was adequate or inadequate (refer to Section 7.6.1 for further detail regarding procedures related to DLTs)
- Any other information deemed relevant by the physician investigator authorizing the treatment and by the physician(s) providing follow up care
- If any other treatment (eg, atropine and/or benzodiazepine) is provided, the drug name, reason(s) for administration, dose and time given, and route of administration will be recorded for each.

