11.1.6. Neuropsychiatric/Behavioral/Cognitive Assessments

The SCID-5-CT (customized) ([First et al-2015](#)) will be administered by a psychologist at Day-1 as a screening tool to exclude any subjects with major DSM-5 Axis I or II disorders. Due to the nature of the assessment, the SCID should not be repeated during this study. Therefore, for any subject who receives the SCID on Day -1, but is subsequently designated an alternate and readmitted on another day, the initial SCID will serve as their assessment of record.

Other assessments of neuropsychiatric/behavioral symptoms will be performed by appropriately experienced and trained study staff using the C-SSRS ([Posner et al-2011](#)), BPRS (expanded version 4.0, 24 items) ([Ventura et al-1993](#)), and RASS ([Sessler et al-2002](#), [Ely et al-2003](#)). A psychiatrist will be available by phone to consult with the investigator throughout the study. At the investigator's request, the psychiatrist will come to the clinic to evaluate a subject.

The C-SSRS Baseline/Screening version will be administered by study staff at screening, and the C-SSRS Since Last Visit version will be administered at Day -1 and at follow-up on Day 8.

Scoring and analysis will be performed according to the Columbia-Suicide Severity Rating Scale Scoring and Data Analysis Guide. Study staff administering the C-SSRS will complete C-SSRS training.

The BPRS will be performed by a psychologist or trained clinician at screening, Day -1 (baseline), at 6 (+ 2) hours post dose (timing at the discretion of the investigator), 48 hours post dose (prior to discharge), and on Day 8. For BPRS items assessed over time (eg, items 1, 2, and 3), the period of assessment should be over the prior week, except for assessments performed at 6 and 48 hours post dose, which will be assessed since the prior assessment. The + 2-hour window for the 6-hour post-dose BPRS is intended to allow the investigator some discretion should the assessment need to be delayed. The timing may be dependent on the emergence and severity of neuropsychiatric symptoms. If the investigator determines a subject is incapable of providing valid responses during the + 2-hour window, the reason(s) why the BPRS was delayed or could not be done will be documented in the source documentation.

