12.5. Key Assumptions

Some of the hypothesis testing planned for this study relies on ANOVA, which requires normality and equal variance across dosing levels (homoskedasticity). If the normality assumption for ANOVA does not hold, link functions will be assessed for use in generalized linear models. In the event that no appropriate link function can be identified to attain normality, non-parametric bootstrap replication will be used to generate standard errors for coefficients. The Koenker-Bassett/generalized Breusch-Pagan Test will be used to test the assumption of homoskedasticity. If homoskedasticity is rejected, unequal variance ANOVA will be used with robust (Huber-White) standard errors.

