13.1. Accounting for Missing, Unused, and Spurious Data

Instances of missing data will be reported along with a reason that data is missing. If multiple measurements are collected, a reason for repeat measurement will be recorded, and the data point corresponding to erroneous or incomplete data collection will be censored. Otherwise, all data will be included in the analysis as specified in the SAP. Data collected following administration of rescue medication will be censored in the analysis of endpoints that are likely to be affected by the rescue medications (BPRS, RASS, DSST, C-SSRS). However, injection site VAS scores will not be censored following administration of rescue medications.

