6.6.3 Handling of Other Missing Data

Other than AE data, for which missing will be imputed as the most severe, missing values will not be imputed for statistical summaries or analysis. All planned analyses of non-AE data will be conducted using all available data, including for participants who withdraw, with the exception of data to be censored following administration of rescue medications (as detailed in 6.11). In the event of study termination, all available data will be used for analysis of cohorts with at least one participant receiving the study drug.

Unless indicated otherwise, summary statistics will be reported for observed data only, with the exception of the cases described below.

Partial or incomplete start/end dates of the AEs or concomitant medications will be imputed to help determine treatment-emergent adverse events and prior or concomitant medications.

For incomplete start dates, following imputation rules will be implemented:

- Missing day - Impute as the 1st of the month unless month is same as month of first dose of study drug then impute using the day of first dose date.
- Missing day and month – impute as 1st January unless year is the same as first dose date then impute using the day and month of first dose date.

- Completely missing – impute using the first dose date unless the end date suggests it could have started prior to this in which case impute as 1st January of the same year as the end date.

When imputing a start date, ensure that the new imputed date is sensible i.e. is prior or equal to the end date of the AE or medication.

For incomplete end dates following imputation rules will be implemented:

- Missing day - Impute as the last day of the month unless month and year are the same as the month and year of the end of study, then impute as the end of study date.
- Missing day and month – Impute as 31st December unless year is the same as the year of the end of study date then impute as the end of study date.

Completely Missing – need to look at whether the AE/medication is still ongoing before imputing a date and also when it started in relation to study drug. If the ongoing flag is not missing then assume that AE is still present / medication is still being taken (i.e. do not impute a date). If the AE/medication has stopped and start date is prior to first dose date then impute as the 1st dose date, if it started on or after first dose date then impute as the end of study date.

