performed, otherwise heterogeneous variance ANOVA will be performed, unless bootstrapping is used.

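### Open-ended censoring of BPRS and DSST after rescue removes rescued active subjects from the 48-hour and Day 8 comparisons, for a reason not supported for DSST after Day 1 physostigmine

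*SAP*

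**What the plan says.** SAP 6.3 (Table 7) plans one-sided tests of each dose against all placebo subjects pooled, for change in BPRS (6 hours, 48 hours, Day 8) and change in DSST (48 hours, Day 8). At both DSST time points, all active doses together are also compared with placebo, on change and on the proportion who decline (SAP 6.14.7).

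After physostigmine, atropine, diazepam or lorazepam, SAP 6.11 states: "Data collected after administration of the rescue medication for the BPRS, DSST, and/or RASS will be censored in analyses, though presented descriptively". Protocol 13.1 gives the reason: post-rescue data "will be censored in the analysis of endpoints that are likely to be affected by the rescue medications (BPRS, RASS, DSST, C-SSRS". Neither text says when censoring ends. SAP 6.6.3 adds that, AE data apart, "missing values will not be imputed for statistical summaries or analysis", and it exempts post-rescue scores from its rule of using all available data. Censored therefore means dropped from the test.

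Protocol 9.2.1 ties physostigmine to concern about harm, and lists two specific circumstances: "A rating of severe (ie, score of 5 or greater) on any of the following 5 items on the BPRS", and a RASS score of 3 or more. The same section says: "The effects of physostigmine last only 1-2 hours". No duration is given for the other rescue drugs. Under protocol 11.1.6, BPRS items that are rated over time look back one week, "except for assessments performed at 6 and 48 hours post dose, which will be assessed since the prior assessment".

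On the error term, protocol 12.5 says: "The Koenker-Bassett/generalized Breusch-Pagan Test will be used to test the assumption of homoskedasticity". If variances differ, SAP 6.10 says "otherwise heterogeneous variance ANOVA will be performed, unless bootstrapping is used".

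**The concern.** Rescue happens after dosing, is prompted by acute neuropsychiatric severity, and is expected mainly on active drug. Dropping rescued subjects leaves a comparison of nearly all placebo subjects with the active subjects who did not need rescue. Randomization no longer protects that comparison.

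The stated reason also sits badly with the timing. An effect lasting 1-2 hours on Day 1 does not explain discarding a DSST score at 48 hours or Day 8, and the DSST is in the study to detect persistent impairment. At stake are the estimates and p-values for the 48-hour and Day 8 BPRS and DSST comparisons.

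**Working it through.** **Plan figures reproduced.** SAP 3.5: 1 − (1 − 0.235)^6 = 0.80. SAP Table 7: 90 + 5 + 5 + 10 = 110 tests. SAP 6.8: fifth Benjamini-Hochberg threshold 0.20 × 5/110 = 0.0091. The documents give no power, SD, effect size or rescue rate for BPRS or DSST.

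**Tests affected.** One active subject rescued on Day 1 leaves 2 BPRS and 2 DSST tests for that dose, 2 pooled DSST change tests and 2 Fisher tests: 2 + 2 + 2 + 2 = 8. With rescue at every dose the count is 2×5 + 2×5 + 2 + 2 = 24, or 24/110 = 22%. If rescue precedes the 6-hour BPRS, that test goes too (9, or 29 at every dose).

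**Shift in the estimate.** Score harm as positive. Let u be the unrescued active mean and u + D the rescued mean, with k of n active subjects rescued. The all-subject mean is u + (k/n)D; the censored mean is u. Censoring lowers estimated harm by (k/n)D.

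- k = 2, n = 6, u = 0, D = 1/2/3 SD: 0.33/0.67/1.00 SD becomes 0.
- BPRS, one of six at the protocol's 40-point DLT threshold at 48 hours from a baseline of 25, others unchanged: (40 − 25)/6 = 2.5 points becomes 0.
- Reverse case, rescued back to 0 and others shifted 1 SD: 1.00 − 2/6 = 0.67 SD becomes 1.00.
- BPRS floor: 24 items scored from 1 give a minimum of 24, and eligibility requires 25 or less, so change cannot fall below −1. Censoring one of six can raise the mean by at most (u + 1)/6, which is 0.17 points when u = 0. Material overstatement therefore needs the unrescued subjects to remain raised.

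**Rejection rates.** Assumptions: normal data, SD 1, 10 placebo, five doses of 6, one-sided 5%, effect only in the rescued subjects of one dose; 200,000 simulated trials per case.

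| Rescued | Error term | D=1 | D=2 | D=3 |
|---|---|---|---|---|
| 2 of 6, kept | pooled | 15% | 31% | 49% |
| 2 of 6, kept | heterogeneous | 12% | 18% | 19% |
| 2 of 6, kept | chosen by 5% variance test | 15% | 28% | 35% |
| 1 of 6, kept | pooled | 9% | 14% | 19% |
| 1 of 6, kept | heterogeneous | 8% | 9% | 8% |
| 1 of 6, kept | chosen by 5% variance test | 9% | 13% | 18% |
| 1 or 2 of 6, censored | any | 5% | 5% | 5% |

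- At the 0.0091 threshold, kept against censored: 2 of 6 at D = 2, about 10% against 1% pooled and 3% against 1% heterogeneous; 1 of 6 at D = 3, 5% against 1% and 1% against 1%.
- Expanded cohort (2 of 9, 11 placebo), D = 2/3 kept: 21/32% pooled, 15/18% heterogeneous; censored 5%.
- Reverse case, 2 of 6: 34% kept against 50% censored pooled; 28% against 44% heterogeneous.
- Same 1 SD shift in everyone: no bias; censoring lowers power from 60% to about 50% pooled and from 56% to 44% heterogeneous.
- Fisher test of DSST decline, 30 active against 10 placebo, rescued all decline and others 20%: 2% kept against 1% censored with 2 rescued; 11% against 1% with 6.

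**P-values need not follow the estimate.** Two constructed examples, pooled error, placebo and other doses between −1 and +1:

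- Top-dose changes 0, 0, 0, 0, 1 and a rescued 15: censoring takes the estimate from 16/6 = 2.67 to 0.2 and p from 0.020 to 0.30.
- Top-dose changes 2, 2, 2, 2, 1 and a rescued 15: the estimate falls from 24/6 = 4.0 to 9/5 = 1.8, yet p falls from 0.0006 to 0.00002, because the error term shrinks.

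**Cost of keeping the values.** Under pooled error, power for a 1 SD effect at another dose falls from 60% to 53% (1 of 6 rescued, D = 3) or 49% (2 of 6, D = 3).

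**The case against.** Censoring after rescue is prespecified and can be defended as keeping the antidote's effect out of the comparison. The trial is exploratory and mainly descriptive (SAP 6.1, 6.8). Rescued subjects stay on view: SAP 6.11 presents their scores descriptively, SAP 6.6.1 presents rescue-censored endpoints separately, SAP 6.14.6 displays scores around signal events, and physostigmine rescue for neuropsychiatric symptoms counts as a DLT. Benjamini-Hochberg is the main significance criterion, and at its stricter thresholds the differences are smaller. Two rescues among the first 8 subjects halt dosing for review, so the 2-of-6 case requires dosing to have resumed or already been complete. Keeping an extreme value also costs power at other doses.

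Much of this stands and limits the point. It does not answer it. Dropping rescued subjects does not estimate what would have happened without rescue unless rescue is unrelated to later scores; it estimates the mean of a selected subgroup. Neither document states such a target or plans an analysis that keeps the scores. Descriptive display does not correct an estimate or p-value that will be reported.

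The BPRS objection is partly right. A Day 8 rating may reach back to the acute episode, and a 48-hour rating covers the time since the previous one, so rescue that shortened an episode could influence either. The case is cleaner for DSST, although the listed rescue circumstances are behavioural and a link from rescue to later DSST is plausible rather than shown.

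**Conclusion.** The point holds as a cheap improvement. The rule, the test counts and the (k/n)D shift follow from the documents and arithmetic. The rejection rates rest on assumed SD, D and k, and the normal model is rough for BPRS, which starts near its floor. Keeping the data removes the selection but often adds little power.

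A reader might infer more than the documents support:

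- *That censoring always hides harm.* Estimated harm is understated if rescued subjects stay worse and overstated if they recover better; p-values can move either way.
- *That rescued subjects vanish from the safety record or that escalation could be misled.* DLT and AE summaries and descriptive displays retain them, and neither protocol 12.3 nor SAP 6.7.2 lets the DSMB decide by statistical test.
- *That the rationale fails for every endpoint and drug.* It is unsupported for DSST at 48 hours and Day 8 after Day 1 physostigmine. It is less clear for BPRS, and no duration is given for atropine or the benzodiazepines.
- *That the SAP exempts C-SSRS.* Protocol 13.1 censors it; SAP 6.11 names it in neither its censored nor its uncensored list.

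If nobody is rescued, nothing changes.

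**What to change.** In SAP 6.11 and protocol 13.1, base the 48-hour and Day 8 DSST and BPRS comparisons on observed values regardless of rescue. Report the censored analysis beside them as a sensitivity analysis, with the number censored by dose and time point. Add a note that BPRS ratings may include the acute episode through the look-back period. For comparisons that keep post-rescue values, report the heterogeneous-variance result as well, since one extreme value inflates the pooled error for other doses. At the least, add the analysis that keeps all observed values.

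Separately, state one rule for C-SSRS after rescue and record any difference from the protocol in SAP 6.2.

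The cost is a protocol and SAP amendment with its approvals, and one extra set of runs on data already collected. The downsides are the loss of power at other doses under pooled error, possible residual effect of other rescue drugs, and the BPRS look-back. Showing both analyses lets the reader see how far the results depend on the rule.
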